## Research Objective and Outcomes

The overall objective of this contract is to train, develop, validate and release a digital biomarker-based algorithm that, in COVID-19 PCR or antigen positive patients, within 30 days of a positive test:

1. **Primary Outcome:** predicts likelihood of requiring a stay in hospital of 24 hours or longer
2. **Secondary Outcomes:**
  - a. Predicts likelihood of being admitted to ICU for either non-invasive (CPAP, BiPAP, high flow nasal oxygen), invasive ventilation or vasopressor support.
  - b. Predicts likelihood of death.
3. **Tertiary Outcomes:** Provides successful delivery, setup, daily interface engagement, and compliance with wearing of the device

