**Table 2. Variables collected for analysis**

Table 2. Variables collected for analysis	
Continuously acquired variables	Categorical variables (continued)
1. Respiration rate	13. Age
2. Pulse rate	14. Sex
3. Oxygen saturation	15. Occupation
4. Skin temperature	16. Household make-up (living alone or with people)
5. Step count	17. Other household members with COVID19
6. Activity levels	18. Other household members enrolled in this study
Categorical variables	19. Menopausal state and time since last menstrual cycle / Pregnancy status
7. Symptoms	20. Race/Ethnicity
8. Days when reporting for employment	21. Zip code
9. Outcomes of any SARS-CoV-2/COVID-19 testing	22. BMI (height & weight)
10. Admission to hospital, ICU, death	23. Comorbidities
	24. Acute and Chronic Medication

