### 4. Introduction

#### 4.1. Preface

In the proposed research, we will use Current Health's remote monitoring wearable device to create novel algorithms to help us predict the progression and severity of COVID-19 in individuals that have recently become infected in the community. Risk scores based on demographics, or for patients in hospital, already exist. However, by using continuous remote patient monitoring, in combination with machine learning and data analysis, we hope to predict the risk of an individual infected with COVID-19 requiring hospitalization, intensive care unit (ICU) treatment, or death based on their vital signs while still in the community.

Using a hospital-grade home-based, remote monitoring wearable gives us the opportunity to create a unique and extremely useful tool in predicting and managing the clinical effects of the COVID-19 pandemic. Our algorithm might bridge the gap between demographic models and in-hospital models of disease progression by providing real-time data from the community. If we are successful, this tool could be made available immediately to enable better resource allocation for patients after diagnosis. In addition, it enables patient-centered management, increasing confidence for low and high-risk patients, and those managing their care. The results of this research will provide a database that can be used in future trials to assess treatment efficacy and offer the potential for rapid algorithm iteration in the event of a future pandemic.

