# 5. Study Objectives and Endpoints and Hypotheses

## 5.1. Study Objectives, Endpoints, and Outcomes

The overall objective of this study is to train, develop, validate and release a digital biomarker-based algorithm that, in COVID-19 PCR or antigen positive participants, within 30 days of a positive test:

1. Primary Outcomes:
  - a. Predicts likelihood of requiring a stay in hospital of at least 24 hours
  - b. Predicts likelihood of recovery from COVID-19 defined as:
    - i. For asymptomatic participants: 14 days without symptoms following positive test
    - ii. For symptomatic: at least 14 days since onset of symptoms, with the last three days symptom free
2. Secondary Outcomes:
  - a. Predicts likelihood of being admitted to ICU for either non-invasive (CPAP, BiPAP, high flow nasal oxygen), invasive ventilation or vasopressor support.
  - b. Predicts likelihood of death.
3. Tertiary Outcomes: Successful delivery, setup, daily interface engagement, and compliance with wearing of the device

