### 6.3. Sample Size

By recruiting participants that have already been identified as SARS-CoV-2/COVID-19 positive, we expect that approximately 10% of individuals from each age group will eventually develop severe or critical COVID-19 symptoms and require hospitalization or treatment in an intensive care unit. Currently there are not sufficiently rigorous statistical models for predicting statistical power for machine learning studies. Some of the issues related to sample size for machine learning models have been recently reviewed in the scientific literature. Machine learning models can be trained to find an effect, but it is not clear if the effect is the result of over-fitting and/or poor sample selection. Nested cross-validation and calibration have been proposed to mitigate these issues. Based on extensive prior experience of our group, we expect that 100 events in continuously monitored participants will be sufficient to assess the training performance of the model for early identification of novel digital biomarkers indicative of disease severity as well as future trajectory of the severity of disease. Using the 100 events and approximate 10% event

rate, we determined that testing and training cohorts of 1,000 participants each (2,000 participants total) will be sufficient.

Although not required in observational clinical trials due to no directly measured effect size, sample size calculations were conducted under different circumstances to ensure sample is sufficiently large for a clinical prediction model.

Calculation 1: Sample size required for precise estimation of the overall outcome probability in the target population. In this study a 10% event rate has been estimated. The number of participants required under the assumption this is a true event rate where  $n$  is the required sample size,  $\phi$  is the anticipated outcome proportion, and  $\delta$  is the absolute margin of error.

$$n = \left( \frac{1.96^2}{\delta} \right) \phi(1 - \phi)$$

To estimate the required number of participants to properly observe 10% event rate at margin error of  $\leq 0.05$ :

$$n = \left( \frac{1.96^2}{0.05} \right) 0.1(1 - 0.1) = 139 \text{ participants}$$

This calculation does not represent the main goal of the study, rather is the lowest bar for number of participants for the stated event observation rate.

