## 9. Analysis

### 9.1. Outcome definitions

Study outcomes will be ascertained by the CRA within the study observational period of 30 days or the following 30 days if the participant has not definitively experienced other outcomes of recovery or death.

Primary and secondary outcomes are presented in (5.1) and will be presented as follows.

Description	Variable	Variable Type
Recovery from COVID-19	recovered	Binary: Yes, No
Hospital stay of 24 hours or longer	hospitalized	Binary: Yes, No
ICU admission	icu_admission	Binary: Yes, No
Death	death	Binary: Yes, No

No calculations are necessary to derive primary or secondary outcomes, they all will be directly stated in binary terms.

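### The primary outcome counts any hospital stay of 24 hours or longer and records no reason for admission, although the objective and the 10% event rate concern COVID-19 severity

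*Combined protocol and SAP*

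**What the plan says.** Three places define the primary event, each by duration only:

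- Protocol, Research Objective and Outcomes: the algorithm "predicts likelihood of requiring a stay in hospital of 24 hours or longer".
- SAP 5.1: "Predicts likelihood of requiring a stay in hospital of at least 24 hours".
- SAP 9.1: the variable `hospitalized`, yes or no, described as "Hospital stay of 24 hours or longer".

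SAP 9.1 adds: "No calculations are necessary to derive primary or secondary outcomes, they all will be directly stated in binary terms". Its outcome table has no field for the reason for admission, and no section provides for adjudication of cause.

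The target is narrower. SAP 4.1 wants to "predict the progression and severity of COVID-19 in individuals that have recently become infected in the community". SAP 6.3 rests the 10% event rate on people who "develop severe or critical COVID-19 symptoms and require hospitalization or treatment in an intensive care unit".

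Pregnancy is not an exclusion in either eligibility table. It is asked in the welcome survey, and protocol Table 2 lists it among the analysis variables as "Menopausal state and time since last menstrual cycle / Pregnancy status". Cancer, kidney disease and other comorbidities are collected too.

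**The concern.** The definition and the target do not describe the same event. A participant with mild infection who delivers, or who has a planned operation or planned treatment for a collected comorbidity, meets the coded definition of the primary event without having progressed. Stage 1 sets hospitalization against having no severe disease, and such a participant would satisfy both descriptions. Neighbouring outcomes are more specific: SAP 5.1 ties ICU admission to ventilatory or vasopressor support and gives recovery its own COVID-19 criteria.

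Three things are at stake:

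1. The planned 100 events would mix COVID-19 and unrelated admissions, while the sizing describes only the former.
2. Unrelated events that the model cannot foresee lower the test-set AUC, and SAP 5.2 and 6.4 require it to be significantly above 0.75 before deployment.
3. Unrelated events that follow a collected variable can make that variable look like a COVID-19 risk factor. The held-out test set would not expose this, because its labels carry the same error.

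**Working it through.** **The plan's own figure.** SAP 6.3: 1,000 participants x 0.10 = 100 events per cohort. This reproduces. The supporting figures of 139 and 756 participants also reproduce, from the formulas in protocol Appendix B, and have no bearing on this point.

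**Share of unrelated events.** The documents give no background admission rate, so the 30-day risk b of a non-COVID stay of 24 hours or longer (births included) is assumed. With 100 COVID-19 events and 900 other participants:

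extra events = 900 x b; share = extra / (100 + extra).

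| Assumed b | Extra events | Share of all events |
|---|---|---|
| 0.2% | 1.8 | 1.8% |
| 0.5% | 4.5 | 4.3% |
| 1% | 9 | 8.3% |
| 2% | 18 | 15.3% |

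If the 10% was instead meant as all-cause, the COVID-19 events among the 100 would be 98, 95, 90 or 80. Reaching 100 COVID-19 events would then take 100/(0.10 - b) = 1,021, 1,053, 1,112 or 1,250 participants.

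**Effect on the AUC rule.** If a fraction f of test events is unrelated and scores like non-events, the expected AUC is (1 - f) x AUC + 0.5f. The Hanley-McNeil standard error with m = 100 events and n = 900 non-events is

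SE² = [A(1 - A) + (m - 1)(Q1 - A²) + (n - 1)(Q2 - A²)] / (mn), where Q1 = A/(2 - A) and Q2 = 2A²/(1 + A).

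The chance that the lower 95% limit exceeds 0.75 is about Φ[(A - 0.75)/SE - 1.96]. For an assumed true AUC of 0.82:

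| f | Expected AUC | SE | Chance of passing |
|---|---|---|---|
| 0 | 0.820 | 0.0263 | 76% |
| 5% | 0.804 | 0.0270 | 51% |
| 10% | 0.788 | 0.0277 | 28% |

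**Pregnancy.** Assume 1% to 5% of participants are pregnant, gestation is spread evenly over 280 days, every birth is a stay of 24 hours or longer, and the COVID-19 risk is the same 10%.

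- Births in 30 days per 1,000: 10 x 30/280 = 1.1, up to 50 x 30/280 = 5.4.
- Risk of the coded event in pregnant participants: 1 - 0.9 x (1 - 30/280) = 19.6%.
- Odds ratio against 10%: (0.196/0.804)/(0.1/0.9) = 2.2, with no true COVID-19 effect.
- If the extra 30 days of ascertainment in SAP 9.1 count, births are 2.1 to 10.7, the risk is 29.3% and the odds ratio is 3.7.

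With 20 to 40 pregnant participants and the 30-day risks, Fisher's exact test reaches p < 0.05 only about 30% to 40% of the time. The protocol selects variables partly by statistical significance, so pregnancy would more often than not miss that criterion in a cohort of this size.

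**The case against.** **The documents never say that childbirth or planned admissions count.** That is true. The surrounding text treats hospitalization as a severity outcome, and protocol Study Design describes capturing the result of visits prompted by severe COVID-19 symptoms. The sentence in SAP 9.1 about not needing calculations concerns derivation, not how the CRA decides yes or no. What stands is that nothing limits the outcome to such visits and no reason is recorded, so the definition as written admits other stays.

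**All-cause stay is a legitimate endpoint.** It is objective and avoids attributing cause, partly through a proxy. This has weight, but the plan neither states nor defends that choice, and its sizing describes a different event.

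**A reader might infer that dilution by itself decides the 0.75 rule.** With f = 10%, an AUC of 0.78 becomes 0.752 and 0.76 becomes 0.734. The documents do not support that reading. The rule requires significance: at 0.78 the SE is 0.028 and the lower 95% limit is 0.725; at 0.76 the limit is 0.704. All four values fail, so dilution changes no decision there. It matters for a stronger model, such as the 0.82 example. The formula also treats every unrelated event as unpredictable. Those that follow a collected variable would cost less AUC, although the model would then be predicting something other than COVID-19 severity.

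**A reader might also infer that the network will learn pregnancy as a cause of COVID-19 hospitalization.** That goes too far. Births are few, the protocol fixes directions of effect from literature and clinical knowledge, and it plans calibration and a search for subpopulations with poor prediction. Pregnancy may also carry a true COVID-19 effect, which births would then obscure.

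**Conclusion.** The point holds as a mismatch between the outcome definition and the study's target. The primary event is any stay of 24 hours or longer with no reason recorded, while the objective and the 100 events concern severe COVID-19. Under an assumed background risk of 0.2% to 2%, about 2% to 15% of counted events would be unrelated; the low end is negligible and the high end is not. For an assumed true AUC of 0.82, the chance of meeting the deployment rule would fall from about 76% to 51% at f = 5% and 28% at f = 10%, provided the unrelated events score like non-events. A spurious association for pregnancy or a comorbidity is possible but not shown to be likely. Every contamination figure is an assumption, because the documents give neither an admission rate nor a pregnancy share. The change should be made because it is cheap and the reason for admission may be hard to recover later: the key linking data to participants is destroyed once analysis ends.

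**What to change.** In SAP 5.1 and 9.1:

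1. Have the CRA record the reason for each admission (COVID-19 or respiratory, obstetric, planned, injury, other) at the outcome verification already scheduled in SAP 6.6, using the participant or the next of kin whom eligibility already requires. The CRA should be blind to the algorithm's output.
2. Exclude from the primary event planned admissions and admissions for delivery without a COVID-19 indication. An obstetric admission with a COVID-19 indication stays in.
3. Report the all-cause stay of 24 hours or longer as a sensitivity analysis in the test set.
4. State in SAP 6.3 which of the two definitions the 10% rate refers to.

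The cost is one coded field at an existing contact, plus SAP wording. There would be slightly fewer primary events, and the reason would be partly proxy-reported, which the all-cause analysis helps to check. Injuries and other unplanned non-COVID stays would still count, so label error is reduced rather than removed.

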### 9.2. Study Stages

Study stages will be broken into three sections: pilot, stage 1 training, and stage 2 testing and validation.

#### Pilot

The pilot phase study with 50 participants will test the feasibility of recruitment, trial logistics, observed participant events, timeline to deterioration, and environmental test settings. The primary aim is to make any revisions to recruitment strategy and to the final number of “critical events” (e.g., hospitalization) required. The secondary aims are to produce descriptive statistics on pilot data, understand user issues that could affect study data, and begin formulating the structure of the Bayesian network. Descriptive statistics will include univariate analysis such as frequency, box plots, or histograms, and where appropriate, bivariate analysis on covariates using methods such as regression, Fisher’s exact tests, or chi-squared analyses.

#### Stage 1

The overall aim of Stage 1 is to collect enough data to perform machine learning analytics on data from the Current Health device to create a Bayesian network algorithm that successfully predicts the risk/probability of no severe disease, hospitalization, ICU admission, and death following SARS-CoV2/COVID-19 infection. The outcomes are *not* mutually exclusive categories, and can be hierarchical, i.e., when a participant first goes to hospital and then is admitted to the ICU. Conversely, a participant at risk could experience death without ever being hospitalized. This will be accounted for by calculating probabilities of each outcome and compare the conditional probabilities analyzing the risk of ICU admission, given that hospitalization has already occurred. One thousand participants will be recruited for the training stage.

Once the Bayesian network model is constructed, to account for model variation, that is a model's parameters change depending on the data the model is being given, cross-validation will be performed to ensure model stability and reduce issues with overfitting. Cross validation will only be conducted in the training data, as any cross validation with testing data has been shown in instances not to aid overfitting issues.

## Stage 2

To assess the algorithm performance, algorithm testing on a total of 1,000 participants will be conducted. This cohort of 1,000 testing participants will be held entirely separate from the training participants to avoid any possible data snooping or data mining bias in the study. In machine learning it is typical to obtain initial testing cohort results to determine if the model created from the training data is performing well. After the first 100 participants in the testing cohort are monitored for 30 days, the algorithm will be tested for understanding initial performance. As more participants are recruited into the study, follow up algorithm testing will occur for each 100 participants that are added to the testing cohort. To avoid any potential issues with multiple testing, only the most recent testing metrics (AUC/ROC, PPV, Brier Scores, etc.) will be reported. Therefore, the unique full test set will only be run *once*.

Although the outcome of the participants in the validation set is known, the outcomes will be initially ignored, as if researchers did not know participant outcome. This simulates what researchers know about a participant preceding the participant's outcome. The testing participants' collected variables (demographic, medical history, continuous data from wearable, and symptom data) will be run through the developed algorithm. The algorithm will return probabilities of the study outcomes. The algorithm's probabilities will then be compared with the true outcome of the participant recorded by the CRA.

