## 5.2. Statistical Hypotheses

These study methods are designed to create an algorithm, specifically a Bayesian Network (BN), and then test the statistical accuracy of the developed Bayesian Network and comparison models on the primary and secondary outcomes. The model acceptance criteria and stated hypothesis is the model's ability to predict the primary outcome of hospitalization of study participants with 75% accuracy. The secondary outcomes will be more exploratory with less strict acceptance criteria. The ability to successfully predict secondary outcomes will largely depend on the number of secondary outcomes observed and if it warrants adequate power.

The benchmarks of model performance will be as follows: AUC between 0.50 and 0.55 is poor, 0.55 to 0.65 is moderate, 0.65 to 0.75 is acceptable, and >0.75 is excellent. Brier scores will be used to verify the accuracy of the event prediction during calibration, where a perfect score is 0 and imperfect score is 1. Brier scores will be calculated for each individual prediction, representing one study participant, and an aggregate Brier score for the sequence of predictions of the participant set.

Different specificity and sensitivity levels will need to be considered when creating a feature that automatically triggers notification of study staff to reduce number of unnecessary alarms and alarm fatigue. In addition, the duration of time a patient spends in a high-risk state needs to be considered. For example, if a participant's oxygen saturation levels (SpO2) levels decrease for a brief period, then regain to normal levels, we will evaluate this to determine if it is an indicative of

patient deterioration or not. This will likely be undertaken by generating a rolling average or median of a certain number of time periods,  $t$ , to ascertain a confident deterioration event.

If the model performs statistically significantly better than 75% (AUC >0.75) with reasonable specificity, sensitivity, and calibration the model will be finalized and deployed.

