## 6.4. Statistical Analyses and Stopping Guidance

Analyses will be conducted in three distinct parts of the trial. Analysis following the pilot study of 50 participants including feasibility, adherence rates, univariate and bivariate statistics, and informing structural design of the Bayesian Network. Descriptive statistics will include univariate analysis such as frequency, box plots, or histograms, and where appropriate, bivariate analysis on covariates using methods such as regression, Fisher's exact tests, or chi-squared analyses.

Stages 1 and 2 are covered in more depth (9.1) but generally following a training and testing machine learning design, respectively. Stopping guidance is determined by both recruitment feasibility and model performance. After a total of 2050 participants are reported, the recruitment will stop. If the model performs statistically significantly better than 75% (AUC >0.75) with reasonable specificity, sensitivity, and calibration, the model will be finalized and deployed. Benchmarks were established as reasonable for similar outcomes in literature. If the model does not meet this standard, we will conduct further analysis into where performance failures were most pervasive to decide how performance could best be improved. Adjustments to significance levels due to analysis stages are not relevant to Bayesian methods.

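### SAP 9.2 answers repeated scoring of the test cohort with a reporting rule; the AUC >0.75 deploy test should be tied to one final analysis of a locked model

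*Combined protocol and SAP*

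**What the plan says.** Stage 2 has 1,000 test participants. SAP 9.2 tests the algorithm once the first 100 have been monitored for 30 days, and then "follow up algorithm testing will occur for each 100 participants that are added to the testing cohort". The protocol's Stage 2 section has the same schedule. SAP 9.2 adds a safeguard: "To avoid any potential issues with multiple testing", "only the most recent testing metrics (AUC/ROC, PPV, Brier Scores, etc.) will be reported". It concludes that the complete test set is therefore run a single time.

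The decision rule is in SAP 5.2: "If the model performs statistically significantly better than 75% (AUC >0.75) with reasonable specificity, sensitivity, and calibration the model will be finalized and deployed". SAP 6.4 repeats it. Neither section says at which look it applies. SAP 6.4 also states "Stopping guidance is determined by both recruitment feasibility and model performance", and it dismisses significance-level adjustment across analysis stages as irrelevant to Bayesian methods. SAP 7.2 sets a significance level of 0.05, and SAP 7.1 says that frequentist methods are used alongside Bayesian ones.

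Other text points to a single closing decision. Just before the deploy rule, SAP 6.4 says "After a total of 2050 participants are reported, the recruitment will stop". SAP 6.5 places the final analysis, including validation, after 1,000 validation participants. In SAP 9.2, test data "will be run through the developed algorithm", the two cohorts are kept apart, cross-validation is confined to training data, and the first look is described as a way to gauge early performance.

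**The concern.** Choosing which metrics to publish does not change what was seen or decided along the way. If the deploy criterion can be met at any look, the chance of meeting it wrongly accumulates, and reporting only the last result hides this. If a disappointing look leads to a change in the model, participants already scored have become tuning data, and later metrics that include them are optimistic. Reporting only the latest metrics removes the trace of either event.

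The remark about Bayesian methods does not help, because the rule is itself a significance criterion. The remark may refer only to the three parts of the study (pilot, Stage 1, Stage 2) and not to the per-100 looks, but on either reading it does not exempt the rule. When the standard is missed, SAP 6.4 turns to how performance could be improved and does not say which data would validate a revised model. Stage 2 is the plan's evidence for deploying the algorithm, so the decision should rest on data that have played no part in shaping it.

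**Working it through.** **The plan's own figures.** SAP 6.3 sizes each cohort as 100 events / 0.10 = 1,000, which reproduces. Its two supporting calculations also reproduce: (1.96/0.05)² × 0.1 × 0.9 = 138.3, rounded up to 139; and exp[(−0.508 + 0.259 ln 0.1 + 0.504 ln 30 − ln 0.05)/0.544] = 755.9, or 756. None of these addresses the AUC test, and the documents give no error rate or power for it.

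**Inputs from the SAP.** Looks at n = 100, 200, …, 1,000; 10% events; AUC bar 0.75; level 0.05.

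**Assumptions, because the SAP is silent.** Looks are cumulative. The test is one-sided at 0.025 (upper tail of two-sided 0.05) or 0.05. The interval is DeLong on the raw (Wald) or logit scale. The model is unchanged, scores are binormal, and all 1,000 participants are evaluable.

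**Precision at the first and last look (Hanley–McNeil).** SE² = [A(1−A) + (m−1)(Q1−A²) + (n−1)(Q2−A²)]/(mn), with Q1 = A/(2−A) and Q2 = 2A²/(1+A). At A = 0.75, Q1 = 0.600 and Q2 = 0.643.
- n = 100 (10 events, 90 non-events): SE 0.092, half-width 1.96 × 0.092 = 0.18 (about 0.16 under the binormal model).
- n = 1,000 (100 and 900): SE 0.029, half-width 0.057. The observed AUC must reach 0.75 + 1.645 × 0.0291 = 0.798, or 0.75 + 1.96 × 0.0291 = 0.807.

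**Chance of crossing the AUC criterion when the true AUC is exactly 0.75** (16,000 simulated cohorts, Monte Carlo SE at most 0.4 points; normal theory from 1,000,000 paths):

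| Decision allowed at | Method | One-sided 0.025 | One-sided 0.05 |
|---|---|---|---|
| Any of ten looks | Normal theory | 9.7% | 17.1% |
| Any of ten looks | DeLong, logit | 12.8% | 20.2% |
| Any of ten looks | DeLong, Wald | 18.7% | 26.1% |
| Looks 3 to 10 | DeLong, logit | 8.5% | 14.2% |
| Looks 3 to 10 | DeLong, Wald | 11.6% | 17.7% |
| Final look only | DeLong, logit | 2.7% | 5.2% |
| Final look only | DeLong, Wald | 3.5% | 6.4% |

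Repeat simulations gave values as low as about 12% and 19% at any look, and about 2% and 4% at the final look. The DeLong ranges carried forward are therefore 12–19% and 19–26%, against 2–4% and 4–6.5%. Part of the excess comes from intervals that behave poorly on 10 to 20 events, as the rows for looks 3 to 10 show. A Hanley–McNeil standard error fixed at AUC 0.75 is conservative here: 4.4% and 10.6% at any look, against 1.0% and 2.8% at the last.

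**A model clearly below the bar (true AUC 0.70).** Any-look crossing is about 2–7% across methods and levels, but only 0.4–1.5% at looks 3 to 10 and under 0.1% at the final look alone. Nearly all of this risk needs a decision on the first two looks.

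**What is not modelled.** The accompanying sensitivity, specificity and calibration conditions would lower these figures. Fewer events, possible because SAP 7.3.2 tests only adherent participants, would raise them. Optimism from changing the model after a look is not quantified.

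**The case against.** The strongest reply is that the authors plainly meant one decision. Recruitment stops at a fixed total (50 + 1,000 + 1,000 = 2,050), the final analysis follows 1,000 validation participants, the interim looks are described as gauging early performance, and the full test set is said to be run once. Test data go through an algorithm already developed, on participants kept apart from training. On that reading repeated scoring causes no inflation, and what remains is a missing link between SAP 6.4 and 6.5. This largely stands, and it is the more natural reading.

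A reader might go further and infer that the plan permits deployment at any look, so that its error rate is 12–26%. The documents do not say so; the figures are conditional. A reader might also infer that a model that misses the bar will be revised and re-tested on the same participants. SAP 6.4 says only that failures will be studied to see how performance could improve. Nor can one conclude that no model lock exists. SAP 12 mentions added text on structural and parameter learning, and a section 9.5, neither of which appears in the available SAP, and a lock could be stated there.

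It is also fair that a true AUC of exactly 0.75 is the worst case under the null. By the plan's own benchmarks, a false crossing there deploys a borderline model, not a poor one.

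The reply does not repair SAP 9.2's reasoning: running the test set once is presented as a consequence of a reporting rule, and it is not one.

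**Conclusion.** The point holds as a flaw in the stated safeguard and as an unassigned decision rule. SAP 9.2 claims that reporting only the latest metrics avoids multiple-testing problems, and it does not. SAP 6.4 makes stopping depend partly on performance and waives adjustment, while SAP 5.2 and 6.4 use a significance criterion with no look attached. None of the text favouring a single final decision ties the deploy rule to that analysis, and no available passage locks the model.

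If the intended reading is followed (one test, unchanged model, 1,000 participants), error is about nominal: 2–4% at one-sided 0.025 and 4–6.5% at 0.05. Only if any of ten cumulative looks could trigger deployment does it rise to about 12–19% and 19–26%, given true AUC 0.75, 10% events and DeLong intervals. At true AUC 0.70 it is about 2–7%, nearly all from the first two looks. The SAP should be amended before Stage 2 outcomes are linked to predictions.

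**What to change.** In SAP 5.2, 6.4 and 9.2:

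1. State that the AUC >0.75 deploy test is made once, at the SAP 6.5 final analysis on the full Stage 2 cohort, and name the sidedness and interval method.
2. State that the per-100 looks are descriptive and trigger neither deployment nor a model change.
3. Lock the algorithm (structure, parameters, cut-points) before Stage 2 outcomes are linked. If a lock already exists in SAP text that is not in the available document, cite it in 9.2.
4. Replace the report-only-the-latest reasoning in 9.2, and the sentence in 6.4 that sets adjustment aside for Bayesian methods, with these rules.
5. If the model is nevertheless changed after a look, count only participants enrolled afterwards as validation.

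Items 1 to 4 cost wording and discipline: no extra participants, but the sponsor gives up tuning on test data. Item 5 costs precision if it is used. A change at 500 leaves about 50 events, and the Hanley–McNeil half-width at AUC 0.75 grows from 1.96 × 0.0291 = 0.057 to 1.96 × 0.0412 = 0.081.
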